9.1.2. Secondary Efficacy Assessments

The following secondary efficacy measures will be collected at the times shown in Section 2.

- Body weight: Patients will be weighed on an electronic scale in a light hospital gown at approximately the same time in the morning after an overnight fast and evacuation of any bowel and bladder contents (See Appendix 8). The scale's performance will be monitored at least monthly using standard weights, and records of these assessments will be kept in the study binder.
- HbA1c
- FBG
- Serum lipids, circulating biomarkers (including fasting insulin, glucagon, lipids, free fatty acids, glycerol, β-hydroxy butyrate, fibroblast growth factor-21 [FGF-21], and adiponectin).
- Waist circumference: Waist circumference should be measured at the midpoint between the lower margin of the least palpable rib and the top of the iliac crest. The patient should stand with feet close together, arms at the side and body weight evenly distributed, and should wear little clothing. The patient should be relaxed, and the measurements should be taken at the end of a normal expiration. The measurement should be repeated. If the difference between the 2 measurements exceeds 1 cm, the 2 measurements should be repeated.

9.1.2.1. Exploratory Efficacy Assessments

• Seven-point SMBG profiles consisting of measurements obtained before each meal, approximately 2 hours after each meal, and at bedtime on a day during the week before the scheduled clinic visit. Patients will record their SMBG levels in their diaries, according to instructions. The complete 7-point profile must be collected on a single day.

If a patient does not complete the entire profile on a single day, all 7 points must be collected on a subsequent day.

9.1.3. Appropriateness of Assessments

All efficacy measures are widely used and generally recognized as reliable, accurate, and relevant with respect to the management of T2DM.

9.2. Adverse Events

Investigators are responsible for monitoring the safety of patients who have entered this study and for alerting Lilly or its designee to any event that seems unusual, even if this event may be considered an unanticipated benefit to the patient.

The investigator is responsible for the appropriate medical care of patients during the study.

Investigators must document their review of each laboratory safety report.

The investigator remains responsible for following, through an appropriate health care option, AEs that are serious or otherwise medically important, considered related to the investigational product or the study, or that caused the patient to discontinue the investigational product before completing the study. The patient should be followed until the event resolves, stabilizes with appropriate diagnostic evaluation, or is reasonably explained. The frequency of follow-up evaluations of the AE is left to the discretion of the investigator.

Lack of drug effect is not an AE in clinical studies, because the purpose of the clinical study is to establish drug effect.

After the ICF is signed, study site personnel will record via CRF the occurrence and nature of each patient's preexisting conditions, including clinically significant signs and symptoms of the disease under treatment in the study. In addition, site personnel will record any change in the condition(s) and any new conditions as AEs. Investigators should record their assessment of the potential relatedness of each AE to protocol procedure or investigational product via CRF.

The investigator will interpret and document whether or not an AE has a reasonable possibility of being related to study treatment, study device, or a study procedure, taking into account the disease, concomitant treatment, or pathologies.

A "reasonable possibility" means that there is a cause-and-effect relationship between the investigational product, study device, and/or study procedure and the AE.

The investigator answers yes/no when making this assessment.

In addition to records of observations made at specific times, unexpected signs and symptoms and concomitant medications will be recorded in the clinical trial records throughout the study.

Planned surgeries and nonsurgical interventions should not be reported as AEs unless the underlying medical condition has worsened during the course of the study.

If a patient's investigational product is discontinued as a result of an AE, study site personnel must report this to Lilly or its designee via CRF, clarifying if possible the circumstances leading to any dosage modifications or discontinuations of treatment.

If the AE or SAE is believed to have been caused by a device issue, in addition to recording the relatedness in the CRF, a product complaint must also be reported.

9.2.1. Serious Adverse Events

An SAE is any AE from this study that results in one of the following outcomes:

- Death
- Initial or prolonged inpatient hospitalization
- A life-threatening experience (i.e., immediate risk of dying)
- Persistent or significant disability/incapacity
- Congenital anomaly/birth defect
- Considered significant by the investigator for any other reason: important medical events that may not result in death, be life threatening, or require hospitalization may be considered serious, based upon appropriate medical judgment.
- When a condition related to the investigational device necessitates medical or surgical intervention to preclude either permanent impairment of a body function or permanent damage to a body structure, the serious outcome of "required intervention" will be assigned.

Although all AEs occurring after signing the ICF are recorded in the CRF, SAE reporting begins after the patient has signed the ICF and has received investigational product. However, if an SAE occurs after signing the ICF, but prior to receiving investigational product, it needs to be reported ONLY if it is considered reasonably possibly related to study procedure.

Study site personnel must alert Lilly or its designee of any SAE within 24 hours of investigator awareness of the event via a sponsor-approved method. If alerts are issued via telephone, they are to be immediately followed by official notification on study-specific SAE forms. This 24-hour notification requirement refers to the initial SAE information and all follow-up SAE information.

Pregnancy (during maternal or paternal exposure to investigational product) does not meet the definition of an AE. However, to fulfill regulatory requirements, any pregnancy should be reported following the SAE process to collect data on the outcome for both mother and fetus.

Investigators are not obligated to actively seek AEs or SAEs in subjects once they have discontinued and/or completed the study (the patient summary CRF has been completed). However, if the investigator learns of any SAE, including a death, at any time after a subject has been discharged from the study, and he/she considers the event reasonably possibly related to the study treatment or study participation, the investigator must promptly notify Lilly.

9.2.1.1. Suspected Unexpected Serious Adverse Reactions

Suspected unexpected serious adverse reactions (SUSARs) are serious events that are not listed in the IB and that the investigator identifies as related to investigational product or procedure. United States 21 CFR 312.32 and European Union Clinical Trial Directive 2001/20/EC and the associated detailed guidances or national regulatory requirements in participating countries require the reporting of SUSARs. Lilly has procedures that will be followed for the recording and expedited reporting of SUSARs that are consistent with global regulations and the associated detailed guidances.

9.2.1.2. Adverse Events of Special Interest

The following Adverse Events of Special Interest (AESIs) of varying clinical significance will be used to determine the tolerability of LY3298176 over the range of doses selected for this clinical trial. All AESIs should be captured and reported to Lilly on the AE eCRF or on a specific eCRF, if applicable (see below). Any AESI that meets the definition of an SAE (see Section 9.2.1) must be reported as an SAE.

When any one of the following events occur, Lilly or its designee must be alerted immediately, whether it is assessed as an SAE or not:

- Confirmed pancreatitis or pancreatic cancer
- Any severe injection site reaction or 2 or more moderate injection site reactions occurring a week or more apart
- Any study drug-related hypersensitivity reaction
- Any other TEAE, SAE, or clinically significant laboratory value for which the investigator believes that permanent study drug discontinuation is the appropriate measure to be taken.

9.2.1.2.1. Injection Site Reactions

All injection site reactions and information regarding their time of day, time relative to injection, size, amount of erythema, induration, and pruritus, as well as severity, will be recorded on specific CRFs. In addition, if the reaction is clinically significant, the site should attempt to contact the sponsor for potential follow-up procedures. Injection site reactions do not need to be recorded as AEs as well unless they meet SAE criteria.

9.2.1.2.2. Hypersensitivity Reactions

All hypersensitivity reactions will be reported by the investigator as either AEs or, if any serious criterion is met, as SAEs. Study drug should be temporarily discontinued for any individual suspected of having a severe or serious allergic/hypersensitivity reaction to study drug. Study drug may be restarted if, in the opinion of the investigator, the event was not related to study drug and when/if it is safe to do so. If study drug is permanently discontinued, the patient should remain in the study.

9.2.1.2.3. Hypoglycemia

Hypoglycemia episodes will be recorded on a specific eCRF. Information regarding severity, time of day, and investigator's opinion of relatedness to study drug and procedure will be

recorded. Hypoglycemia episodes should not be recorded as AEs unless the event meets serious criteria. Hypoglycemia will be classified as follows (American Diabetes Association 2005):

- Documented Symptomatic Hypoglycemia: Any time a patient feels that he/she is experiencing symptoms and/or signs associated with hypoglycemia and has a plasma glucose level of ≤3.9 mmol/L (≤70 mg/dL)
- Asymptomatic Hypoglycemia: An event not accompanied by typical symptoms of hypoglycemia, but with ≤3.9 mmol/L (≤70 mg/dL) plasma glucose.
- Severe Hypoglycemia: An episode requiring the assistance of another person to actively administer carbohydrate, glucagon, or other resuscitative actions. These episodes may be associated with sufficient neuroglycopenia to induce seizure or coma. Plasma glucose measurements may not be available during such an event, but neurological recovery attributable to the restoration of plasma glucose to normal is considered sufficient evidence that the event was induced by a low plasma glucose concentration.
- Nocturnal Hypoglycemia: Any hypoglycemic event that occurs between bedtime and waking
- Probable Symptomatic Hypoglycemia: An event during which symptoms of hypoglycemia are not accompanied by a plasma glucose determination (but that was presumably caused by a plasma glucose concentration ≤3.9 mmol/L [≤70 mg/dL]).

9.2.1.2.4. Nausea, Vomiting, and Diarrhea

Nausea, vomiting, and diarrhea events will be recorded on a specific eCRF. They should not be recorded as AEs unless the event meets an SAE criterion. For each event, assessment of severity, duration, and Investigator's opinion of relatedness to study drug and protocol procedure will be captured.

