PRO patient-reported outcomes

QTc corrected QT interval

QW once weekly

SAD single ascending dose

SAE serious adverse event **SAP** statistical analysis plan

SC subcutaneous

Screen The act of determining if an individual meets minimum requirements to become part of

a pool of potential candidates for participation in a clinical study.

SD standard deviation

SDP single-dose pen

SMBG self-monitoring of blood glucose

SmPC Summary of Product Characteristics

SUSAR suspected unexpected serious adverse reactions

T2DM type 2 diabetes mellitus

TE-ADA treatment-emergent antidrug antibodies

TEAE Treatment-emergent adverse event: An untoward medical occurrence that emerges

during a defined treatment period, having been absent pretreatment, or worsens relative

to the pretreatment state, which and does not necessarily have to have a causal

relationship with this treatment.

TIA transient ischemic attack

ULN upper limit of normal (reference range)

USPI United States Package Insert

WHO World Health Organization

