6.10.4. Adverse Events of Special Interest

Adverse events of special interest to be identified and described during this study are injection site reactions, hypersensitivity reactions, hypoglycemia, acute pancreatitis, major adverse CV events, and selected GI events (nausea, vomiting, and diarrhea).

Descriptive statistics for AESIs will be presented by treatment group and visit. Continuous responses will be summarized using sample size, mean, SD, median, minimum and maximum, while categorical responses will be summarized using sample size, frequency and percentage.

If data warrant, continuous elements of AESIs (such as the duration of hypoglycemaic events) will be analyzed using an MMRM-based model described in Section 6.1.1.

In addition, for AESIs with information collected on the AE eCRF page (that is, hypersensitivity reactions, acute pancreatitis, and major adverse CV events) summary tables will be presented only if >3% of patients has the AESI. The incidence of patients with at least 1 AESI and the patient incidence of AESIs will be summarized, showing frequency and percentage of patients, by SOC (if applicable), PT, and treatment group. The total number of AESIs and the number of AESIs for each SOC (if applicable) and PT will also be reported for each treatment group.

Listings by patient will be provided for AESIs. Listings will also present adjudication information by patient for adjudicated events.

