6.10.4.2. Injection Site Reactions

Injection site reactions are collected in a questionnaire. The following items or other available categories may be collected and summarized for each injection site reaction:

- pain
- itching
- rash
- reaction timing
- swelling
- redness
- erythema
- bruising
- hematoma.

Injection site reactions which meet SAE criteria will also be collected as AEs. If >3% patients have such event occur, then these injection site reactions may be summarized by PT using the version of Medical Dictionary for Regulatory Activities (MedDRA) current at the time of programming.

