6.10.4.3. Nausea, Vomiting, and Diarrhea

Nausea, vomiting, and diarrhea event information will be collected on a designated separate eCRF page.

The incidence of nausea, vomiting, and diarrhea will be summarized by the treatment and the time interval of interest. The duration of each event will also be computed in days as event stop date minus event start date. For computation purposes, the end date for ongoing events is the date of last study contact.

The maximum severity and duration from baseline to Week 26 of nausea, vomiting, and diarrhea will be summarized by treatments.

Plot with the % number of subjects with the events vs initiation time course by day and week will also be generated. The y-axis is the % subjects with the specified AE and the x-axis is the time in day or week since the first dose.

A listing with GI TEAEs of interest will be provided.

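### Do the general adverse event and registry tables miss non-serious nausea, vomiting and diarrhea because these are recorded on their own form?

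*Protocol*

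**What the plan says.** Two recording rules in the protocol matter. For nausea, vomiting and diarrhea, section 9.2.1.2.4 calls for a specific eCRF and adds: "They should not be recorded as AEs unless the event meets an SAE criterion". For injection site reactions, section 9.2.1.2.1 is looser: "Injection site reactions do not need to be recorded as AEs as well unless they meet SAE criteria".

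The SAP follows the same split. Section 6.10.4.3 says: "Nausea, vomiting, and diarrhea event information will be collected on a designated separate eCRF page". Section 6.10.4.2 takes injection site reactions from a questionnaire and says of those that meet serious criteria: "If >3% patients have such event occur, then these injection site reactions may be summarized by PT". When section 6.10.4 names the events of special interest that sit on the AE page, it lists neither group: "for AESIs with information collected on the AE eCRF page (that is, hypersensitivity reactions, acute pancreatitis, and major adverse CV events".

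SAP 6.10.3 defines a TEAE by timing and worsening. The tables in 6.10.3.1 to 6.10.3.5 then count TEAEs by preferred term. SAP 6.15 defines the registry's Other category as events that are TEAEs and not serious. Table 6.8 has a row for coded injection site reactions. None of these places names a source form or a rule for merging forms.

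SAP 6.10.4 also gives a general commitment covering all events of special interest: "Descriptive statistics for AESIs will be presented by treatment group and visit".

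**The concern.** Read literally and in sequence, the two documents could produce safety tables that look complete but are not. A programmer who builds the TEAE dataset from the AE page alone would find only serious nausea, vomiting and diarrhea there. The any-TEAE, maximum-severity, related, most-common and registry Other tables would then leave out the non-serious cases. The registry table is the sharpest case: it is restricted to non-serious events, which is exactly the class that protocol 9.2.1.2.4 keeps off the AE page for these three terms.

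Gastrointestinal tolerability is a named secondary aim, and the trial supports Phase 3 dose selection. A separate table cannot repair the any-TEAE or related-TEAE patient counts, because patients with these events overlap with patients who have other events.

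**Working it through.** There is no planned figure to reproduce. The check sets the passages side by side and then asks what each reading would produce.

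**1. Does any section state an AE-page-only build?** No. The two rules tell sites where to write an event down. The injection-site rule speaks of AE entry in addition to the specific form, which reads as a guard against double entry.

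**2. Text pointing to inclusion.**
- Protocol 9.2.1.2 lets an event of special interest be reported on the AE form or on a specific form.
- Protocol 10.3.4.1 counts events of special interest within TEAEs.
- Protocol 8.1.2 uses nausea and vomiting as its example of an AE.
- Protocol Appendix 1 defines a TEAE without reference to any form: "An untoward medical occurrence that emerges" during treatment, or that worsens.
- SAP 6.10.4.3 ends its account of the dedicated-form events with "A listing with GI TEAEs of interest will be provided", and its plot axis calls them AEs.
- SAP 6.11.4.4 describes the Table 6.8 events as TEAEs and gives injection site reactions their own row.

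**3. Text pointing to separate reporting.**
- SAP 6.10 lists events of special interest beside TEAEs rather than within them.
- SAP 6.10.4.2 mentions preferred-term summaries only for injection site reactions that meet serious criteria.

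The text is mixed, with more of it on the side of inclusion.

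**4. Could the analysts merge the records?** For nausea, vomiting and diarrhea, yes. Protocol 9.2.1.2.4 collects severity, duration and relatedness. SAP 6.10.4.3 computes duration from start and stop dates, so onset dates exist. Those fields are enough for treatment-emergence, maximum severity, relatedness and patient counts, and the three events are already named as single terms.

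**5. What would the AE-page reading do?** Protocol 10.1 randomizes about 300 patients to six arms, and SAP 6.10.3.5 sets a 5% threshold in any LY3298176 arm.
- Patients per arm: 300 / 6 = 50.
- Threshold: 0.05 × 50 = 2.5, so 3 patients qualify (3/50 = 6.0%) and 2 do not (2/50 = 4.0%).
- A gastrointestinal term would therefore need 3 patients with a serious event in one arm. The documents give no incidence, so the table assumes a range:

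| Assumed incidence | Patients of 50 | Serious share needed |
|---|---|---|
| 10% | 5 | 3/5 = 60% |
| 20% | 10 | 3/10 = 30% |
| 40% | 20 | 3/20 = 15% |

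On this reading the registry Other table would hold none of the three terms if sites keep to the rule. The reach is five tables plus one row of Table 6.8. The two discontinuation tables cannot be judged, because the form's fields are not shown in full.

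**6. What is reported either way?** SAP 6.10.4.3 gives incidence by treatment and time interval, maximum severity, duration, onset plots and a listing. SAP 6.10.4 adds descriptive statistics by group and visit. Its 3% gate applies to the AE-page events only, so it does not suppress the gastrointestinal summaries.

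**The case for a change.** The strongest case for a change is that two competent programmers could follow this SAP and produce different tables, which is a weakness whichever reading was meant. It is strongest for the registry, where the Other category is defined as non-serious TEAEs and no dedicated summary can stand in for it. Stating the source would be cheap, since the records are already collected.

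That the SAP is silent stands. That it is in error does not follow: the harm needs an AE-page-only build that neither document specifies. The registry definition also rests on what a TEAE is, not on the page it was written on, so applying it as written favors inclusion.

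Three further arguments are weaker than they look.
- A nearly empty injection-site row in Table 6.8 is not established. Protocol 9.2.1.2.1 permits AE entries for non-serious reactions, so capture would be uneven rather than absent.
- Protocol 9.8.1 uses association with a moderate to severe injection site reaction as a patient-level criterion for antibody follow-up. Nothing ties that decision to Table 6.8.
- Requiring all dedicated-form data to be merged is a preference. Injection site reactions come from a questionnaire of items such as pain, itching and redness, so one reaction could generate several preferred terms. Non-serious hypoglycemia is kept off the AE page by the same kind of rule (protocol 9.2.1.2.3) and is reported separately in SAP 6.10.4.4 without difficulty.

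**Conclusion.** No change to the plan follows. The SAP leaves open whether dedicated-form records enter its general TEAE tables, its registry tables and Table 6.8, but no stated rule is shown to give a wrong result. SAP 7.1 provides for building the tabulation and analysis datasets, and this mapping is an ordinary decision at that step. The dates, severity and relatedness needed for the three gastrointestinal terms are collected.

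The effect is zero if the records are merged. If they are not, it is confined to five tables for non-serious nausea, vomiting and diarrhea, with uneven capture of injection site reactions there and in one row of Table 6.8. Other gastrointestinal events are outside the rule. The number of events affected cannot be given, and the shares in the table above rest on assumed incidences.

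This conclusion assumes that the analysts apply the form-independent TEAE definition, or else keep the separate reporting visible as SAP 6.10.4 plans. The eCRF pages and dataset specifications, which would settle the matter, are not among the documents.

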9.2.1.2.5. Acute Pancreatitis

Acute pancreatitis is defined as an AE of interest for this study. Acute pancreatitis is an acute inflammatory process of the pancreas that may also involve peripancreatic tissues and/or remote organ systems(Banks et al. 2006). The diagnosis of acute pancreatitis requires 2 of the following 3 features:

- abdominal pain, characteristic of acute pancreatitis (generally located in the epigastrium and radiates to the back in approximately half the cases [Banks et al. 2006; Koizumi et al. 2006]; the pain is often associated with nausea and vomiting);
- serum amylase (total and/or pancreatic) and/or lipase $\ge 3 \times ULN$;
- characteristic findings of acute pancreatitis on computed tomography (CT) scan or magnetic resonance imaging (MRI).

If acute pancreatitis is suspected, appropriate laboratory tests (including levels of pancreatic amylase and lipase) should be obtained via the central laboratory (and locally, if needed). Imaging studies, such as abdominal CT scan with or without contrast, MRI, or gallbladder ultrasound, should be performed. If laboratory values and/or abdominal imaging support the diagnosis of acute pancreatitis, the patient must discontinue therapy with investigational product,

but will continue in the study on another glucose-lowering regimen (see Section 7.8.1 for details on rescue intervention). The most appropriate diabetes therapeutic regimen will be decided by the investigator, based on the patient's clinical status. A review of the patient's concomitant medications should be conducted to assess any potential causal relationship with pancreatitis.

Each case of AE of pancreatitis must be reported. If typical signs and/or symptoms of pancreatitis are present and confirmed by laboratory values (lipase or amylase [total and/or pancreatic]) and imaging studies, the event must be reported as an SAE. For a potential case that does not meet all of these criteria, it is up to the investigator to determine the seriousness of the case (AE or SAE) and the relatedness of the event to study drug.

In addition to the diagnostic assessment in patients who develop symptoms of acute pancreatitis, each patient will have measurements of pancreatic amylase and lipase at screening, baseline, and at each non-PK-specific visit to assess any potential effects of LY3298176 on the exocrine pancreas (refer to Section 2, Schedule of Activities). Further diagnostic assessment per Lilly algorithm for assessment of asymptomatic pancreatic hyperenzymemia will be required whenever lipase and/or pancreatic amylase are ≥3× ULN at any time during the study. If this situation occurs at Visit 801 (Week 30), the patient will be required to undergo this additional workup, and the data will be collected in the clinical trial database.

All suspected cases of acute or chronic pancreatitis, as well as cases of confirmed lipase or pancreatic amylase values ≥3× ULN, will be adjudicated by an independent committee of expert physicians. In addition, AEs of severe or serious abdominal pain of unknown etiology will also be submitted to the adjudication committee to assess for possible pancreatitis or other pancreatic disease. Relevant data from patients with acute or chronic pancreatitis, those with severe or serious abdominal pain, and those that undergo additional assessments due to confirmed hyperenzymemia will be entered into a specifically designed eCRF page by study site or Lilly staff. The adjudication committee representative will enter the results of adjudication in a corresponding eCRF page.

